10.7. Physical Examination

At screening, weight and height will be recorded and a physical examination will be performed, followed by a brief physical examination at baseline (pre-infusion on Day 1) and Day 30. Any changes from the screening and baseline visit to Day 30 will be recorded. Full and brief physical examination will include the following assessments:

Assessment	Full physical examination	Brief physical examination
General appearance	X	X
Head, ears, eyes, nose, throat	X	-
Cardiovascular	X	X
Respiratory	X	X
Gastrointestinal	X	X
Dermatological	X	-
Neurological	X	-
Musculoskeletal	X	-
Lymphatic	X	-
Other (at the investigator's discretion)	X	X

Body systems will be classified as "Normal", "Abnormal Clinically Significant" and "Abnormal Not Clinically Significant". Shift tables comparing physical examination results from baseline to last assessment will be presented by treatment.

Physical examination data will also be listed.

This document is confidential.

11. Interim Analyses

An interim analysis for efficacy (including ECG and Holter ECG), PK/PD, safety and tolerability will be conducted after all randomised patients have been recruited into Part 1 of the study and either completed Day 2 or terminated the study.

Interim Analysis at End of Part 1:

During the first IA the following will occur, regardless of the response seen for the AP30663 3 mg/kg dose:

- Dose 3 (3 mg/kg AP30663) will be stopped.
- Dose 5 (5 mg/kg AP30663 versus placebo) will be opened.

Additionally, the following decision will be made dependent on the response rate seen for 3 mg/kg AP30663:

- If the proportion of patients achieving a response under AP30663 3 mg/kg is > 0.65 then Dose 2 (2 mg/kg AP30663) will additionally be opened for Part 2 (in parallel to Dose 5).

Interim Analyses during Part 2:

Interim analyses will occur when 18, 36 and 54 randomised patients have completed Day 2 assessments or terminated the study in Part 2. At these IAs the following rules will be utilised:

- a) If an open Dose d has at least 10 randomised patients having completed Day 2 assessments and satisfies: $(P_d > 0.65) \geq 0.90$ then Dose d will be closed for sufficient efficacy response.
 - If the dose one level below this dose has never been opened, then dose d-1 is opened.
- b) If an open Dose d has at least 10 randomised patients having completed Day 2 assessments and satisfies $(P_d > 0.65) < 0.10$ then Dose d will be closed.
 - If Dose d was the largest dose thus far open, and Dose d is < 6 mg/kg, then dose d + 1 will be opened.

The study will continue until all doses of AP30663 have been closed or the maximum of 72 patients during Part 2 (up to 108 patients total across Part 1 and Part 2) have been enrolled.

While the algorithm, and the DMC's decision for dose increase/decrease, is based on AF conversion rate only, the DMC will also convene to review safety and tolerability data at defined time points; review of this data may also lead to further decisions being made by the DMC.

This document is confidential.

12. Changes from Analysis Planned in Protocol

None

This document is confidential.

13. Reference List

None

This document is confidential.

14. Programming Considerations

All tables, figures, listings (TFLs), and statistical analyses will be generated using SAS for Windows, Release 9.4. (SAS Institute Inc., Cary, NC, USA). Computer-generated table, listing and figure output will adhere to the following specifications.

The static analysis based on plasma concentration will be performed using a non-compartmental analysis (NCA), the PK analyses will be performed by Syneos Health using Phoenix WinNonlin® (release 8.0 or higher) and all other analyses and summaries will be produced using Statistical Analysis System (SAS®) version 9.4 (or higher).

PK analyses will be performed using NONMEM® version 7.4.

14.1. General Considerations

- One SAS program can create several outputs
- One output file can contain several outputs.
- Output files will be delivered in Rich Text Format (RTF) that can be manipulated in MSWord
- Numbering of TFLs will follow ICH E3 guidance

14.2. Table, Listing, and Figure Format

14.2.1. General

- All TFLs will be produced in landscape format on A4 paper size, unless otherwise specified.
- All TFLs will be produced using the Courier New font, size 8, which is the smallest acceptable point size for the Regulatory Authorities.
- The data displays for all TFLs will have a minimum blank 1-inch margin on all 4 sides.
- Headers and footers for figures will be in Courier New font, size 8, which is the smallest acceptable point size for the Regulatory Authorities.
- Legends will be used for all figures with more than 1 variable, group, or item displayed.
- TFLs will be in black and white (no color), unless otherwise specified.
- Specialized text styles, such as bolding, italics, borders, shading, and superscripted and subscripted text, will not be used in the TFLs, unless otherwise specified. On some occasions, superscripts 1, 2, or 3 may be used (see below).
- Only standard keyboard characters will be used in the TFLs. Special characters, such as non-printable control characters, printer-specific, or font-specific characters, will not be used. Hexadecimal-derived characters will be used, where possible, if they are appropriate to help

This document is confidential.

display math symbols (e.g., μ). Certain subscripts and superscripts (e.g., cm^2 , C_{max}) will be employed on a case-by-case basis.

- Mixed case will be used for all titles, footnotes, column headers, and programmer-supplied formats, as appropriate.

14.2.2. Headers

- All output should have the following header at the top left of each page:
 - Acesion Pharma ApS
- Protocol: AP30663 - 2001
- Draft/Final Run <date>
- All output should have Page n of N at the top or bottom right corner of each page. TFLs are internally paginated in relation to the total length (i.e., the page number should appear sequentially as page n of N, where N is the total number of pages in the table).
- The date/time of the generation of the output should appear along with the program name as a footer on each page.

14.2.3. Display Titles

- Each TFL is identified by the designation and a numeral. (i.e., Table 14.1.1). ICH E3 numbering. A decimal system (x.y and x.y.z) are used to identify TFLs with related contents. The title is centered. The analysis set are identified on the line immediately following the title. The title and table designation are single spaced. A solid line spanning the margins will separate the display titles from the
- Column headers. There will be 1 blank line between the last title and the solid line.

Table x.y.z
First Line of Title
Second Line of Title if Needed
FAS Analysis Set

14.2.4. Column Headers

- Column headings are displayed immediately below the solid line described above in initial upper-case characters.
- In the case of efficacy tables, the variable (or characteristic) column will be on the far left followed by the treatment group columns and total column (if applicable). P-values may be presented under the total column or in separate p-value column (if applicable). Within-treatment comparisons may have p-values presented in a row beneath the summary statistics for that treatment.

This document is confidential.

- For numeric variables, include "unit" in column or row heading when appropriate.
- Analysis set sizes will be presented for each treatment group in the column heading as (N=xx) (or in the row headings, if applicable). This is distinct from the 'n' used for the descriptive statistics representing the number of patients in the analysis set.
- The order of treatments in the tables and listings will be Placebo first in the case of placebo controlled studies and Active comparators first in the case of active comparator trials, followed by a total column (if applicable).

14.2.5. Body of the Data Display

14.2.5.1. General Conventions

Data in columns of a table or listing are formatted as follows:

- Alphanumeric values are left-justified;
- Whole numbers (e.g., counts) are right-justified; and
- Numbers containing fractional portions are decimal aligned.

14.2.5.2. Table Conventions

- Units will be included where available
- If the categories of a parameter are ordered, then all categories between the maximum and minimum category are presented in the table, even if n=0 for all treatment groups in a given category that is between the minimum and maximum level for that parameter. For example, the frequency distribution for symptom severity would appear as:

Severity Rating	N
severe	0
moderate	8
mild	3

Where percentages are presented in these tables, zero percentages will not be presented and so counts of 0 will be presented as 0 and not as 0 (0%).

- If the categories are not ordered (e.g., Medical History, Reasons for Discontinuation from the Study, etc.), then only those categories for which there is at least 1 patient represented in 1 or more groups are included.
- An Unknown or Missing category are added to each parameter for which information is not available for 1 or more patient.

This document is confidential.

- Unless otherwise specified, the estimated mean and median for a set of values are printed out to 1 more significant digit than the original values, and standard deviations are printed out to 2 more significant digits than the original values. The minimum and maximum should report the same significant digits as the original values. For example, for systolic blood pressure:

N	XX
Mean	XXX.X
Std Dev	X.XX
Median	XXX.X
Minimum	XXX
Maximum	XXX

- P-values are output in the format: "0.xxx", where xxx is the value rounded to 3 decimal places. Every p-value less than 0.001 will be presented as <0.001. If the p-value are less than 0.0001, then present as <0.0001. If the p-value is returned as >0.999, then present as >0.999
- Percentage values are printed to one decimal place, in parentheses with no spaces, one space after the count (e.g., 7 (12.8), 13 (5.4)). Unless otherwise noted, for all percentages, the number of patients in the analysis set for the treatment group who have an observation will be the denominator. Percentages after zero counts should not be displayed and percentages equating to 100% are presented as 100%, without decimal places.
- The percentage of of patients is normally calculated as a proportion of the number of patients assessed in the relevant treatment group (or overall) for the analysis set presented. However, careful consideration is required in many instances due to the complicated nature of selecting the denominator, usually the appropriate number of patients exposed. Describe details of this in footnotes or programming notes.
- For categorical summaries (number and percentage of patients) where a patient can be included in more than one category, describe in a footnote or programming note if the patient are included in the summary statistics for all relevant categories or just 1 category and the criteria for selecting the criteria.
- Where a category with a subheading (such as system organ class) has to be split over more than one page, output the subheading followed by "(cont)" at the top of each subsequent page. The overall summary statistics for the subheading should only be output on the first relevant page.

14.2.5.3. Listing Conventions

- Listings will be sorted for presentation in order of treatment groups as above, patient number, visit/collection day, and visit/collection time.
- Dates are printed in SAS DATE9.format ("ddMMMyyyy": 01JUL2000). Missing portions of dates are represented on patient listings as dashes (--JUL2000).

This document is confidential.

- All observed time values are to be presented using a 24-hour clock HH:MM or HH:MM:SS format (e.g., 11:26:45, or 11:26). Time will only be reported if it was measured as part of the study.
- Units will be included where available

14.2.5.4. Figure Conventions

- Unless otherwise specified, for all figures, study visits will be displayed on the X-axis and endpoint (e.g., treatment mean change from Baseline) values will be displayed on the Y-axis.

14.2.6. Footnotes

- A solid line spanning the margins will separate the body of the data display from the footnotes.
- All footnotes will be left justified with single-line spacing immediately below the solid line underneath the data display.
- Footnotes should always begin with "Note:" if an informational footnote, or 1, 2, 3, etc. if a reference footnote. Each new footnote should start on a new line, where possible.
- Patient specific footnotes are avoided, where possible.
- Footnotes will be used sparingly and add value to the table, figure, or listing. If more than six lines of footnotes are planned, then a cover page is strongly recommended to be used to display footnotes, and only those essential to comprehension of the data will be repeated on each page.
- The last line of the footnote section will be a standard source line that indicates the name of the program used to produce the data display, date/time the program was run, and the listing source (i.e., 'Program : myprogram.sas Listing source: 16.x.y.z').

This document is confidential.

15. Quality Control

SAS programs are developed to produce output such as analysis data sets, summary tables, data listings, figures or statistical analyses. An overview of the development of programs is detailed in Syneos Health SOP Developing Statistical Programs (3907).

Syneos Health SOPs Developing Statistical Programs (3907) and Conducting the Transfer of Biostatistical Deliverables (3908) describes the quality control procedures that are performed for all SAS programs and output. Quality control is defined here as the operational techniques and activities undertaken to verify that the SAS programs produce the output by checking for their logic, efficiency and commenting and by review of the produced output."

This document is confidential.

16. Index of Tables

Table Number	Name	Analysis Set	Delivered for Interim analysis/DMC
Table 14.1.1.1	Patient Disposition	Enrolled Set	
Table 14.1.1.2	Patient Disposition – Cohort only	Enrolled Set	Only for IA
Table 14.1.2.	Major Protocol Deviations	Randomised Set	
Table 14.1.3.1.1	Demographics	Safety Set	✓
Table 14.1.3.1.2	Demographics – Cohort only	Safety Set	Only for IA
Table 14.1.3.2	Baseline Characteristics	Safety Set	
Table 14.1.3.3	Medical /Surgical History	Safety Set	
Table 14.1.4.1	Prior Medications	Safety Set	
Table 14.1.4.2	Concomitant Medications	Safety Set	
Table 14.1.5.1	Exposure to Study Treatment	Safety Set	✓
Table 14.1.5.2	Compliance with Study Treatment	Safety Set	
Table 14.2.1.1.1	Conversion from AF within 90 Minutes from Start of Infusion : Summary of Response Rate, Bayesian Model	Full Analysis Set	✓
Table 14.2.1.1.2	Conversion from AF within 90 Minutes from Start of Infusion : Summary of Response Rate, Bayesian Model	Per Protocol Set	
Table 14.2.1.1.3	Conversion from AF within 90 Minutes from Start of Infusion : Summary of Response Rate, Logistic Regression	Full Analysis Set	✓
Table 14.2.1.1.4	Conversion from AF within 90 minutes from start of infusion : Summary of Response Rate, Logistic Regression	Per Protocol Set	
Table 14.2.2.1.1	Time to Conversion from AF – Descriptive Statistics, Kaplan-Meier Analysis	Full Analysis Set	✓
Table 14.2.2.1.2	Time to Conversion from AF – Descriptive Statistics, Kaplan-Meier Analysis	Per Protocol Set	
Table 14.2.2.2.1	Relapse of AF within 5 min following Pharmacological or DC Conversion – Summary of relapse rate - Logistic Regression	Full Analysis Set	
Table 14.2.2.2.2	Relapse of AF within 5 min following pharmacological or DC conversion – Summary of relapse rate	Per Protocol Set	

This document is confidential.

Table Number	Name	Analysis Set	Delivered for Interim analysis/DMC
Table 14.2.2.2.3	Relapse of AF within 5 min following Pharmacological Conversion – Summary of relapse rate - Logistic Regression	Full Analysis Set	
Table 14.2.2.2.4	Relapse of AF within 5 min following Pharmacological Conversion – Summary of relapse rate - Logistic Regression	Per Protocol Set	
Table 14.2.2.3.1	Proportion of Patients in SR after Start of Infusion at Different Timepoints - Logistic Regression	Full Analysis Set	✓
Table 14.2.2.3.2	Proportion of Patients in SR after Start of Infusion at Different Timepoints - Logistic Regression	Per Protocol Set	
Table 14.2.3.1	Descriptive Statistics of Plasma Concentration over Time by Treatment	PK Set	
Table 14.2.3.2	Summary of Pharmacokinetic Parameters – NCA Approach	PK Set	
Table 14.3.1.1	Overall Summary of Treatment-Emergent Adverse Events	Safety Set	✓
Table 14.3.1.2	Treatment-Emergent Adverse Events by System Organ Class and Preferred Term	Safety Set	
Table 14.3.1.3	Treatment-Emergent Adverse Events Related to Study Treatment	Safety Set	✓
Table 14.3.1.4	Serious Treatment-Emergent Adverse Events by System Organ Class and Preferred Term	Safety Set	✓
Table 14.3.1.5	Treatment-Emergent Adverse Events Leading to Study Discontinuation by System Organ Class and Preferred Term	Safety Set	
Table 14.3.1.6	Treatment-Emergent Adverse Events by System Organ Class, Preferred Term, and Maximum Severity	Safety Set	
Table 14.3.4.1.1.1	Summary statistics of Laboratory Data: Haematology	Safety Set	
Table 14.3.4.1.1.2	Change from Baseline in Laboratory Data: Haematology	Safety Set	
Table 14.3.4.1.1.3	Laboratory Data: Haematology Relationship to Reference Range – Shift from Baseline	Safety Set	

This document is confidential.

Table Number	Name	Analysis Set	Delivered for Interim analysis/DMC
Table 14.3.4.1.1.4	Laboratory Data: Haematology Clinical Significance	Safety Set	
Table 14.3.4.1.2.1	Summary statistics of Laboratory Data: Clinical Chemistry	Safety Set	
Table 14.3.4.1.2.2	Change from Baseline in Laboratory Data: Clinical Chemistry	Safety Set	
Table 14.3.4.1.2.3	Laboratory Data: Clinical Chemistry Relationship to Reference Range – Shift from Baseline	Safety Set	
Table 14.3.4.1.2.4	Laboratory Data: Clinical Chemistry Clinical Significance	Safety Set	
Table 14.3.4.2.1	Summary of Vital Signs	Safety Set	
Table 14.3.4.2.2	Change from Baseline in Vital Signs	Safety Set	✓
Table 14.3.4.3.1	Summary of 12-Lead ECG Parameters	Safety Set	
Table 14.3.4.3.2	Change from Baseline in 12-Lead ECG Parameters	Safety Set	✓
Table 14.3.4.3.3	12-Lead ECG Clinical Significance	Safety Set	✓
Table 14.3.4.3.4	12-Lead ECG QTc Intervals: Categorical Analysis	Safety Set	✓
Table 14.3.4.4	Brief Physical Examination - Shift from Baseline	Safety Set	

This document is confidential.

17. Index of Figures

Figure Number	Figure Title	Delivered for Interim analysis/DMC
Figure 14.2.2.1.3	Kaplan-Meier curve for Time to Conversion from AF – Full analysis set	
Figure 14.2.3.3	Mean (\pm SD) Plasma Concentration - Linear and Semi-Log Scales - PK Set	✓ For interim analysis this graph will be provided by the PK group
Figure 14.2.3.4	Overlay of Individual and Mean AP30663 Plasma Concentrations by Treatment - Linear and Semi-Log Scales - PK Set	✓ For interim analysis this graph will be provided by the PK group
Figure 14.2.3.5	Scatter plot of Plasma Concentration Immediately After Conversion versus Time to Conversion – PK set	
Figure 14.2.3.6	Mean (\pm SD) Cmax vs. AP30663 Dose Level - PK Set	
Figure 14.2.3.7	Mean (\pm SD) AUC0-t vs. AP30663 Dose Level - PK Set	
Figure 14.2.3.8	Mean (\pm SD) AUC0-0.5 vs. AP30663 Dose Level - PK Set	
Figure 14.2.3.9	Scatter Plot of Cmax vs. Time to Conversion - PK Set	
Figure 14.2.3.10	Scatter Plot of AUC0-t vs. time to conversion- PK Set	
Figure 14.2.3.11	Scatter Plot of AUC0-0.5 vs. Time to Conversion - PK Set	
Figure 14.2.3.12	Bar chart of conversion rate vs. Age – Full analysis set	
Figure 14.2.3.13	Bar chart of conversion rate vs. Gender – Full analysis set	
Figure 14.2.3.14	Bar chart of conversion rate vs. Left Atrial Dimension/Diameter (Anterior Posterior, End Systolic)– Full analysis set	
Figure 14.2.3.15	Bar chart of Conversion Rate vs. Duration of Current AF episode– Full Analysis Set	

This document is confidential.

Figure Number	Figure Title	Delivered for Interim analysis/DMC
Figure 14.2.3.16	Bar Chart of Conversion Rate vs. Treatment Group – Full Analysis Set	

This document is confidential.

18. Index of Listings

Table Number	Name	Analysis Set	Delivered for Interim analysis/DMC
Listing 16.2.1.1	Completion of Study/Withdrawal of Study	Enrolled Set	
Listing 16.2.2	Protocol Deviations	Randomised Set	
Listing 16.2.3.1	Inclusion/Exclusion Criteria not met	Randomised Set	
Listing 16.2.3.2	Patients Excluded from Analysis Set	Randomised Set	
Listing 16.2.4.1	Demographics	Safety Set	
Listing 16.2.4.2	Baseline Characteristics	Safety Set	
Listing 16.2.4.3	Medical/Surgical History	Safety Set	
Listing 16.2.4.4	Prior and Concomitant Medications	Safety Set	
Listing 16.2.5.1	Study Drug Administration	Safety Set	
Listing 16.2.6.1	Efficacy : Conversion	Full Analysis Set	
Listing 16.2.7.1	Adverse Events	Safety Set	
Listing 16.2.7.2	Serious Adverse Events	Safety Set	
Listing 16.2.7.3	Adverse Events Leading to Treatment Discontinuation	Safety Set	
Listing 16.2.8.1.1	Haematology	Safety Set	
Listing 16.2.8.1.2	Clinical chemistry	Safety Set	
Listing 16.2.8.2.	Vital Signs	Safety Set	✓ Based on Randomised Set
Listing 16.2.8.3.	12-Lead ECG	Safety Set	✓ Based on Randomised Set
Listing 16.2.8.4	Physical Examination	Safety Set	
Listing 16.2.8.5	Plasma concentrations	PK Set	
Listing 16.2.8.6	Pharmacokinetics Parameters – NCA Approach	PK SET	

This document is confidential.

19. Appendices

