9.3 Day 1 – During Infusion

When all the baseline procedures have been performed and the investigator has confirmed the patient's eligibility for the study, study drug will be administered as a single intravenous infusion for 30 min on Day 1. The following procedures will be performed during infusion on Day 1:

- Administer study drug as intravenous infusion.

¹ Note, if the patient is found eligible, the randomisation should be planned in such a way that all logistics will occur in the protocol-specified timeframe, including timely reconstitution of study drug, infusion start and – if applicable - DC cardioversion in non-responders within 180 min from infusion start.

- Record any AEs that have occurred since the pre-infusion status and any changes in concomitant medication. Special attention should be paid to monitoring for AEs related to the central nervous system including tremors. Please also refer to section 8.2.4.2 for stop of infusion criteria.
- Record vital signs ([semi]supine BP, heart rate, heart rhythm from ECG).
- Collect PK plasma samples 5 min \pm 1 min, 15 min \pm 1 min, 25 min \pm 1 min, and 30 min - 1 min after start of infusion. The infusion should not be stopped before the 30 min - 1 min PK sample has been collected. In the case of conversion from atrial fibrillation during infusion, an additional PK sample will be taken immediately after conversion.
- Perform a 12-lead digital ECG (with ECG print-outs 10 min after infusion start and, in case of conversion from AF, within 1 min after conversion BUT before infusion stop).
- Continue 12-lead Holter monitoring.
- Continue telemetry.

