2.2. Timings of Analyses

The study will be conducted in two parts (Parts 1 and 2): Part 1 of the study is a fixed randomisation placebo-controlled parallel design, and Part 2 will be an adaptive design conducted in one or more further doses of AP30663 vs Placebo.

In Part 1 of the study, up to 36 patients will be randomised in a 1:1 ratio to receive AP30663 at 3 mg/kg or matching placebo. An interim analysis (IA) will be conducted once the randomised patients in Part 1 have completed Day 2 assessments or terminated the study (see section 8.1 of the protocol).

An interim analysis (Part 1) including efficacy, PK/PD, safety and tolerability data will be conducted after all randomised patients have completed Day 2 assessments of the study, in order to determine the starting dose(s) for Part 2 of the study. For further information see section 11. An independent data monitoring committee (DMC) will be convened to review the accumulating unblinded efficacy (including ECG and Holter ECG), PK/PD, safety and tolerability data for the study at the time of the interim analysis.

During Part 2, IAs will occur when 18, 36 and 54 patients have been randomised to open-doses including placebo, and have completed Day 2 assessments or terminated the study.

For Part 2, the DMC will give their recommendations regarding continuation or early termination of the study. Decision rules will be based on the AF conversion rate; however the DMC will also have the option to stop a dose arm (or the study) due to unacceptable safety and tolerability (including but not limited to increase in QTcF interval and number and severity of local injection site reactions).

An unblinded team (unblinded statistician and unblinded programming team) will be responsible for generating and delivering unblinded TFLs to the DMC members. Tables that will be delivered for the interim analysis are detailed in Section 16.

This document is confidential.

3. Study Objectives

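### Under the SAP's delivery list, a non-serious adverse event reaches the DMC by name only if the blinded investigator did not grade it unlikely or unrelated; the all-causality table should be added to the interim package.

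*SAP*

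**What the plan says.** SAP Section 2.2 points to one place for the content of the interim package: "Tables that will be delivered for the interim analysis are detailed in Section 16".

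The Section 16 index has a column for delivery to the interim analysis and DMC. Its TEAE rows read as follows.

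- Marked: 14.3.1.1, "Overall Summary of Treatment-Emergent Adverse Events"; 14.3.1.3, "Treatment-Emergent Adverse Events Related to Study Treatment"; and 14.3.1.4, "Serious Treatment-Emergent Adverse Events by System Organ Class and Preferred Term".
- Not marked: 14.3.1.2, "Treatment-Emergent Adverse Events by System Organ Class and Preferred Term"; 14.3.1.5, "Treatment-Emergent Adverse Events Leading to Study Discontinuation by System Organ Class and Preferred Term"; and 14.3.1.6, "Treatment-Emergent Adverse Events by System Organ Class, Preferred Term, and Maximum Severity".

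In SAP Section 18, none of the three adverse event listings (16.2.7.1 to 16.2.7.3) is marked; only the vital-sign and 12-lead ECG listings are. Compliance Table 14.1.5.2 is not marked either. SAP Section 10.2, on compliance, is where reasons for stopping the infusion are summarised.

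Causality is assigned by the investigator (Protocol 10.1.3.1), who stays blinded (Protocol 8.4.7). SAP Section 10.3 counts possible, probable, very likely and missing causality as related, and unlikely and unrelated as not related.

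On CNS events, Protocol 9.3 says: "Special attention should be paid to monitoring for AEs related to the central nervous system including tremors". Protocol 8.3.4.2 lists tremor among the criteria for stopping the infusion. SAP Section 2.2 lets the DMC stop an arm or the study for unacceptable safety and tolerability. It names QTcF and injection site reactions as examples and does not limit the remit to them.

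**The concern.** Together, these rules leave the related-event table as the only marked adverse event output that can name a non-serious event. The DMC is the body that sees safety data by arm, and in a randomised comparison an all-causality count by arm lets the allocation do the attribution. The related-event table instead passes each event through a case-by-case judgement made without knowledge of the arm, and drops those that fail it before the unblinded reviewers see them.

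The DMC advises on escalation and on stopping arms from small cohorts, where one or two cases missing from a named term can change how the term reads. CNS events are the clearest example because the protocol asks sites to watch for them. The same holds for any non-serious term.

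**Working it through.** The plan states no figure for this point, so there is none to reproduce. The check is a reading of the delivery column, followed by an illustration of size.

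**Step 1: follow a non-serious tremor graded unlikely or unrelated through the marked outputs.**

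- Table 14.3.1.1 (overall TEAE summary): counted; the title indicates no breakdown by term.
- Table 14.3.1.3 (related): excluded under SAP 10.3.
- Table 14.3.1.4 (serious): excluded, because it is not serious.
- Table 14.1.5.1 (exposure, marked): if the infusion was cut short, the shorter duration may show, but not the reason.
- Table 14.1.5.2 (compliance), which would carry the reason: not marked.
- Listing 16.2.7.1 (adverse events): not marked.

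So 3 of 6 TEAE tables and 0 of 3 adverse event listings are delivered, and this event is not named in any of them. Blank cells are read as not delivered; marks survive on neighbouring rows, so loss in text extraction is unlikely. The title of 14.3.1.3 does not mention preferred terms, but SAP 10.3 says adverse event summaries are by SOC and preferred term. If this one were not, no non-serious event would be named at all.

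**Step 2: arm sizes.** Protocol 8.1 randomises Part 2 cohorts of 18 in a 2:1 ratio. With one open dose, 18 × 2/3 = 12 new active patients and 6 placebo. With two open doses, 6 patients each and 6 placebo. Placebo accumulates to 18 + 6 = 24 at the first Part 2 interim if Part 1 is full, as in the examples in Protocol 17.3.

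**Step 3: chance of seeing few of the true cases.** Assume 3 patients at a dose have a drug-caused non-serious CNS event, each called related independently with probability r. The number named to the DMC is X ~ Binomial(3, r), so

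P(X ≤ 1) = (1 − r)³ + 3r(1 − r)².

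- r = 0.5: 0.125 + 0.375 = 0.50
- r = 0.7: 0.027 + 0.189 = 0.216
- r = 0.9: 0.001 + 0.027 = 0.028

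With Table 14.3.1.2 delivered, all 3 are named whatever r is. The documents give neither r nor the number of true cases; both are assumptions.

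**Step 4: the same question with the case count random.** Assume a true rate of 25% among 12 patients (3 expected). The chance that at least 2 are named, from Binomial(12, 0.25 × r), is 0.84, 0.69, 0.45 or 0.17 for r = 1, 0.75, 0.5 or 0.25. With 6 patients per dose it is 0.47, 0.31, 0.17 or 0.05. Delivering 14.3.1.2 corresponds to r = 1.

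**Step 5: effect on a comparison.** A hypothetical split of 4/12 active against 1/24 placebo has a one-sided Fisher p of 0.034. If only one active case and no placebo case is called related, the table shows 1/12 against 0/24, with p = 0.33. This is an extreme case: it loses three of the four active cases.

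**The case against.** The strongest reply is that few events would be lost. Protocol 10.1.3.1 defines *possible* as reasonable timing together with another credible explanation, and SAP 10.3 counts that as related. An alternative explanation alone therefore does not remove a well-timed event. *Unlikely* requires timing that makes a causal link improbable. A tremor during a 30-minute infusion would ordinarily be graded at least possible. This stands, and it makes r = 0.9 more credible than 0.5 for events during the infusion.

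A reader might infer that the DC shock and its sedation would be blamed for such events. The documents do not support this for tremor during the infusion: cardioversion is for AF persisting 90 minutes after infusion start (Protocol 8.4.8.2). It could apply only to later events.

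A CNS excess is also not expected from the documents. Protocol Section 6 reports no CNS effects in Phase 1, including tremor measurement, in healthy men at doses up to 8 mg/kg. The assumed 3 in 12 therefore has no empirical basis here.

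A reader might infer that the all-causality table is the only unbiased safety comparison available, or that the related-event table is biased. Neither follows. The DMC also receives, by arm and regardless of attribution, the overall TEAE summary, serious events by term, exposure, vital-sign changes and ECG tables. Attribution made blind to arm thins events in every arm, so its main cost is sensitivity.

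Finally, a reader might infer that the data are withheld from the DMC. That cannot be shown. Protocol 10.2 leaves the data to be reviewed to the DMC Charter, which is not among the documents, and Protocol 11.1.6 lets recommendations draw on other available data. What stands against this reply is that SAP 2.2 states what will be delivered, and a reader of the SAP cannot tell that more is.

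**Conclusion.** The point holds for the SAP's own delivery list. Non-serious events graded unlikely or unrelated are not named in the interim package and appear at most within a total. The gap is real but partial: it excludes serious events, events graded possible or higher, and events with missing causality.

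The size depends on an attribution rate the documents do not give. With 3 true cases, the chance that at most one is named runs from 0.50 at r = 0.5 to 0.03 at r = 0.9. The upper end of the r range suits events during the infusion; lower values are more plausible for later events with competing causes. These figures illustrate lost sensitivity and do not predict a CNS signal.

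A change is still worthwhile, because the protocol itself flags these events, the DMC's safety remit is open-ended, and each Part 2 cohort adds only about 6 to 12 patients per open dose. The index is also out of step with the remit elsewhere: the DMC is to weigh the severity of injection site reactions, yet severity Table 14.3.1.6 is not marked.

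**What to change.** In SAP Section 16, mark Table 14.3.1.2 (all-causality TEAEs by SOC and preferred term, by arm) for every interim, and keep Table 14.3.1.3 as supportive. Then align SAP Sections 16 to 18 with the DMC Charter, so that both name the same outputs. In that alignment, settle whether severity Table 14.3.1.6, compliance Table 14.1.5.2 and Listing 16.2.7.1 also go to the DMC. If the Charter already provides the all-causality table, a cross-reference in the SAP is enough.

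The cost is one more run per interim of a table already planned for the final analysis, by the unblinded team that already produces the related and serious event tables. No dose, stopping rule, endpoint or site blinding changes.
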